### 2.9.3 Acceptability

**Participant in-depth interviews:** We will interview up to 36 participants recruited through a purposive sampling strategy to obtain a maximum variation sample by strategy arm, transition in care status, timing of ART initiation, and age group. In-depth interviews will be conducted by trained experienced research assistants in the participant's preferred language (e.g., Sepedi, isiZulu, isiXhosa, and Sesotho). Interviews will explore:

- Perceptions of the care model they were assigned to
- Interactions with other patients (either at a TCAC or traditional care)
- Family and relationship status, housing stability, and sources of support (financial, social, emotional)
- Experiences with HIV and other (non-HIV and non-allopathic) service providers, including perceived or experienced stigma related to their HIV or ex-inmate status, and v) ideas about what services they still need.

**Staff and TCAC facilitator in-depth interviews:** We will interview approximately 12 staff members involved in TCAC referral, implementation, or coordination (sample size based on the anticipated number of individuals to have substantial involvement in transition in care in facilities and the community). Interviews will explore: i) Comfort with referring to TCAC and ii) adaptability of TCAC to routine operations.

## 3 Drugs/substances/devices

Study participants will receive standard-of-care (SOC) ARV (anti-retroviral) drugs to treat HIV infection that will be dispensed at the DoH primary care clinics or pre-packed by Department of Health primary care clinics.

## 4 Study statistics

---

### 4.1 Sample size

As a study of feasibility and acceptability we have selected a sample size that, based on prior experience, can easily be recruited within 6 months. From the most recent prior work, we recruited approximately 35 inmates per month (approximately 2% declined participation). Over a 6 month period this would result in 210 *released* inmates. To be conservative, we will seek to recruit only 50% of the recruitment rate of the prior study, representing a total of 60 participants into the standard of care and 120 in the TCAC arm. We will continue recruiting until we have reached 180 released inmates.

**Table 4 : Sample size for TCAC evaluation**

Arm	Sample size
Care as usual	60
TCAC	120

Recruiting 120 in the TCAC arm will provide four TCACs with 12-20 participants each (assuming 40 to 66% successful transition in care to TCACs among participants in that arm). The 1:2 enrollment provides a greater population in the TCAC arm for assessing acceptability. This sample size has an 80% power with an alpha of 0.05 to identify an approximate difference in proportion meeting the primary outcome (in care with an undetectable viral load at 6 months) of 0.24 (e.g. 0.25 versus 0.49 meeting the primary outcome) assuming successful outcome ascertainment for 78% of participants (our success in a prior study) (Figure 2). We note that this is not an effectiveness study and we present these calculations purely to illustrate the power.

[figure not shown]

Figure 2: Proportions in care in CAU and TCAC that study is powered to detect with alpha of 0.05

## 4.2 Analysis

### 4.2.1 Feasibility

Success will be based on *a priori* targets of  $\geq 90\%$  of those attempting to attend a TCAC session able to find the location, successful follow-up of  $\geq 75\%$  of participants (based on the challenging nature of follow-up of this population our prior work with 75% follow-up), and viral load ascertainment for  $\geq 95\%$  of participants in care.

### 4.2.2 Effectiveness

Effectiveness will be based on intention to treat comparing CAU and intervention group outcomes using assessed using mixed effects logistic regression with correctional facility included as a mixed effect.

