#### 2.4.2 Randomization

We will perform individual randomization blocked by correctional facility. Study staff will open numbered envelopes with the allocation following enrollment. Participants will be randomized 1:2 to either the standard of care or the TCAC using sequential envelopes with study arm determination sealed inside (blocked by study site and based on random number generation). Participants and members of the research team recruiting and implementing the strategy will be unmasked to randomization assignment due to the behavioral nature of the strategy and need for team members to explain the study arm procedures to participants. Study assignments will be masked to staff performing outcome assessments and the investigators until all outcome data have been collected.

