#### 2.5.2 TCAC study arm

Participants will have a pre-release session with a study team member. The goal of the session is to review contact from the study team or contacting the study team following release, update any changes in contact information, and to encourage post-release linkage to care. In addition, participants will be reminded of the location and timing of the TCAC session that they have been assigned to and will be provided a contact number for a TCAC facilitator. At release the TCAC arm will also receive a referral letter describing ART regimen and a supply of ART (per DCS routine).

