## 2.8.8 TCAC content

A schematic intervention-impact diagram is shown below in Figure 1.

[figure not shown]

Figure 1: Intervention impact model

Part 1: Group discussion and group cognitive behavioral training.

The first 45-60 minutes will involve facilitated discussions among participants related to issues salient to the group. The facilitation of these sessions will seek to teach cognitive behavioral approaches. These approaches can be applied by a participant toward what is most salient to him or her. This may include managing depression, harm reduction, or medication adherence. The overall method is through group cognitive behavioral therapy.

Each session will include discussion on topics of salience to the group such as substance use, alcohol use, ART adherence, family and community relationships, and employment readiness. Facilitation will seek to have participation and involvement from all group members in sharing experiences, strategies, and resources.

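### The TCAC arm is treated in about four clubs, but the planned tests and the 80% power allow no within-club correlation; if there is any, the interval is too narrow and the power overstated

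*Combined protocol and SAP*

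**What the plan says.** Section 2.4.2 sets the unit of randomization: "We will perform individual randomization blocked by correctional facility". It also sets the ratio: "Participants will be randomized 1:2 to either the standard of care or the TCAC". Section 4.1 gives the numbers, "representing a total of 60 participants into the standard of care and 120 in the TCAC arm".

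The intervention is delivered to groups. Before release, TCAC participants are "reminded of the location and timing of the TCAC session that they have been assigned to" (section 2.5.2). Of the discussion part of each session, section 2.8.8 says: "The overall method is through group cognitive behavioral therapy". The text under Table 4 adds: "Recruiting 120 in the TCAC arm will provide four TCACs with 12-20 participants each". That rests on 40 to 66% of the arm moving into a club. Section 2.5.1 describes no grouping for CAU.

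For the analysis, Table 3 lists a chi-square test of the primary outcome. Section 4.2.2 describes "comparing CAU and intervention group outcomes using assessed using mixed effects logistic regression with correctional facility included as a mixed effect". On power, the text under Table 4 states: "This sample size has an 80% power with an alpha of 0.05". The example is 0.25 versus 0.49 with outcomes known for 78% of participants, and the authors label the calculation as illustrative. Club as a cluster, an ICC and a design effect are not mentioned anywhere.

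**The concern.** This is a partially nested design: individuals are randomized, but only one arm is then treated in groups. TCAC visits count towards the primary outcome (section 2.9.2), so a club that is hard to reach, or runs well or badly, can shift the outcome of many members together. Outcomes may therefore be correlated within clubs in the TCAC arm and not in CAU.

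The facility effect in section 4.2.2 does not stand in for this. Randomization is blocked by facility, so both arms are present in each facility, whereas clubs form in the community after release.

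Two things are at stake. One is the precision claimed for the TCAC versus CAU difference, which belongs to a primary objective (section 1.2). The other is the planning of the full RCT that this pilot is meant to prepare. A larger trial delivered through clubs needs a club ICC, and this plan neither models nor reports one.

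**Working it through.** **Inputs.** 60 CAU and 120 TCAC, 0.25 versus 0.49, 78% ascertainment, four clubs, 40-66% reaching a club (all section 4.1 and the text under Table 4). Two-sided alpha of 0.05 is assumed, because the plan does not state sidedness. The ICC values 0.02, 0.05 and 0.10 are assumed.

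**Reproducing the 80%.** Analysed: n1 = 0.78 × 60 = 46.8 and n2 = 0.78 × 120 = 93.6.
- Pooled proportion: (46.8 × 0.25 + 93.6 × 0.49)/140.4 = 0.41.
- Null SE: √[0.41 × 0.59 × (1/46.8 + 1/93.6)] = 0.0881.
- Alternative SE: √[0.25 × 0.75/46.8 + 0.49 × 0.51/93.6] = 0.0817.
- Power: Φ[(0.24 − 1.96 × 0.0881)/0.0817] = Φ(0.825) = 79.5%.

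The stated figure is matched with no design effect.

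**Adding a club effect.** Let f be the fraction of the analysed TCAC arm that is correlated within clubs, with m = 93.6f/4 per club.
- Design effect for the arm: DE = f[1 + (m − 1)ICC] + (1 − f).
- Power: the formula above with n2 replaced by 93.6/DE.
- True over assumed SE under the null, since n2 = 2n1: R = √[(2 + DE)/3].
- Type I error of the unadjusted test: 2[1 − Φ(1.96/R)].

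| Correlated share f (m) | ICC | DE | Effective TCAC n | R | Type I error | Power |
|---|---|---|---|---|---|---|
| 0.40 (9.36) | 0.02 | 1.07 | 87.7 | 1.01 | 5.3% | 78.6% |
| | 0.05 | 1.17 | 80.2 | 1.03 | 5.6% | 77.3% |
| | 0.10 | 1.33 | 70.1 | 1.05 | 6.3% | 75.2% |
| 0.66 (15.4) | 0.02 | 1.19 | 78.6 | 1.03 | 5.7% | 77.0% |
| | 0.05 | 1.48 | 63.4 | 1.08 | 6.9% | 73.5% |
| | 0.10 | 1.95 | 47.9 | 1.15 | 8.8% | 68.2% |
| 1 (23.4) | 0.02 | 1.45 | 64.6 | 1.07 | 6.8% | 73.8% |
| | 0.05 | 2.12 | 44.2 | 1.17 | 9.4% | 66.5% |
| | 0.10 | 3.24 | 28.9 | 1.32 | 13.8% | 57.1% |

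**Simulation check.** Beta-binomial simulation of the unadjusted test gives type I error of 5.1-5.6% / 5.4-6.9% / 6.0-8.7% at ICC 0.02 / 0.05 / 0.10 when only attenders are correlated, and about 6.5-7% / 9.5% / 14% for the whole arm.

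**Two sensitivities.**
- The first two blocks assume that attenders and non-attenders are ascertained equally. If instead all 48-80 attenders (12-20 in each of four clubs) are among the 93.6 analysed, power is 78.0-75.3% / 75.9-69.7% / 72.4-61.9%.
- The table makes no charge for estimating the club variance from four clubs. For the whole arm, an unpooled test with Satterthwaite degrees of freedom has power of about 70% / 58% / 44%, against 79% at ICC 0 by the same method.

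**The case against.** The strongest reply is that this is a pilot. The plan calls its power figures illustrative and its effectiveness assessment preliminary, and section 6.7 sets no stopping criterion for effectiveness. No confirmatory decision rests on this p-value. That stands, and it limits the weight of the point. It does not remove it, because the comparison with CAU is a listed primary objective with a planned test.

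Second, a reader might infer that standard errors are certainly too small and that all 120 participants are treated together. The documents do not support either. A positive ICC is plausible but not documented. The power rests on about 94 analysed participants, and the plan expects only 48-80 of the 120 to join a club. At 40% attendance and ICC 0.02, power falls by less than one percentage point.

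Third, a reader might infer that each club has its own site, clinic and pair of facilitators. Sections 2.8.2 and 2.8.6 describe TCACs as affiliated with a clinic and led by two facilitators, without saying whether clubs share them. Sharing could reduce the variation between clubs.

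Fourth, the inflated type I error needs a particular null: clubs whose effects differ but average to zero. If clubs affect nobody, individual randomization keeps the chi-square test near 5%.

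Fifth, four clubs say little about an ICC. In simulation with four clubs of 23 and a true ICC of 0.02, the estimate was zero or negative in 43% of runs, with a 95% range of −0.04 to 0.15. This is why the fix asks for fixed-ICC intervals as well as an estimate.

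Against the second point, non-attendance may itself depend on the club, for example on its location. Counting attenders only could then understate the clustering.

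**Conclusion.** The concern holds conditionally. The chi-square test, the mixed logistic model and the 80% power all set the club ICC to zero without saying so. If the ICC is positive, the confidence interval is too narrow and the power overstated.

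On the plan's own attendance assumption, with ICC 0.02 / 0.05 / 0.10:
- Type I error is about 5.1-5.6% / 5.4-6.9% / 6.0-8.7%.
- Power is about 79-77% / 77-73% / 75-68%, against 79.5% as planned.

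As an upper bound, with the whole arm correlated, type I error is about 6.5-7% / 9.5% / 14% and power about 74% / 66% / 57%, before any small-sample penalty.

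These sizes rest on an assumed ICC range, four clubs of equal size and, for the attender figures, equal ascertainment. The plan should be changed. A reading that the effectiveness comparison is invalid would go too far for a pilot with this declared purpose.

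**What to change.** **Section 4.2.2.** Record the assigned club for every TCAC participant at allocation, including those who never attend, since it may not be recoverable later. Analyse the effectiveness comparison by assigned club, with a club variance component in the TCAC arm only and small-sample degrees of freedom. If that variance is estimated at zero, also show the interval at fixed ICC 0.02 and 0.05. Report the club ICC with its interval for planning the full RCT, and note its imprecision. I would not add adjustment for site, which is debatable with four clubs.

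**Section 4.1.** State that 80% assumes a club ICC of 0, and give the power at 0.02, 0.05 and 0.10 with the attendance assumption used.

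**Cost.** One recorded variable, analysis wording and a restated power figure. Sample size, treatment and follow-up do not change. The price is a wider interval for the comparison and an ICC that will be imprecise.

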**Barriers to the transition from corrections to community care:** Post-release, ex-inmates are expected to use the referral letter to establish care with Department of Health (DoH) clinics. It is the responsibility of the ex-inmate to identify the clinic and the appropriate days to go, and to advocate for his or her care. There is no active follow-up provided by DCS or DoH to confirm a successful transition, nor is there specific coordination between the DCS and the DoH regarding the release of ex-inmates receiving HIV care. Because of the absence of formal communication between the DCS and the DoH there is no documentation of the transition of care from corrections to community care to inform patient care, care continuum indicators, or quality improvement. The impressive HIV care outcomes observed in correctional settings in South Africa drop off dramatically following release from corrections. Ex-inmates living with HIV encounter unique care transition challenges across the socio-ecological framework. Qualitative and quantitative research conducted by the PI ([name]) and co-I ([name]) with 492 ex-inmates in South Africa, identified several important themes related to the transition in care among ex-inmates. These include the clinic experience, social capital, stigma, substance use (11% of participants with identified drug use), re-incarceration, and economic insecurity. Depression also affects the transition from corrections to community care in the United States, but has not been evaluated in this context in South Africa. Substance use is another barrier to the care transition. Substance use itself interferes with care seeking due to increased impulsivity as well as diminished social capital. As a result of these barriers, at 6-months following release, only 44% had continuity in antiretroviral therapy ([name] unpublished data).

**Barriers to care engagement in the general population in Africa:** Experience with the general population living with HIV provides additional insight regarding potential barriers for ex-inmates. On the individual level of the socio-ecological model, knowledge of HIV, self-efficacy, fatalism,

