### 2.5 Pre-release study procedures

All participants will have a baseline demographic, health, and incarceration history questionnaire. In addition the ASSIST substance use tool, social capital questionnaire, and stigma index will be used with all participants. Participants will have a second pre-release contact with study staff if release is more than one week from enrollment. The purpose of this visit will be to review the study, the allocation arm, and to encourage linking to care following release.

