**Table 3: Effectiveness outcomes**

Primary outcome	Self-reported in care at six months by arm	Test of proportions (chi-square)
Secondary outcomes	Self-reported linkage to care by 90 days by arm	Test of proportions (chi-square)
	Clinical record verified in care at six months by arm	Test of proportions (chi-square)
	HIV RNA <400c/mL for those in care by arm	Test of proportions (chi-square)
	Social capital score by arm	Test of medians (Wilcoxon rank sum)
	Stigma index score by arm	Test of medians (Wilcoxon rank sum)
	Employed or self-employed by arm	Test of proportions (chi-square)

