### 5.1 Data collection tools

**Table 5: List of data collection tools and intended use**

Name of tool	Purpose	Schedule	Study arm
Visit Contact Documentation (AD001)	To collect and track information on all study contacts made with the participant during scheduled visit windows.	Pre-release Post-release	CAU TCAC
Pre-release locator Form (AD002)	To collect the participant's personal information important for identifying and contacting the participant for follow up after release.	Pre-release	CAU TCAC
Release Verification (AD003)	To verify participant release from the correctional facility and collect information of the documented date of release.	Post-release	CAU TCAC
Post-release locator Form (AD004)	To collect the participant's personal information important for identifying and contacting the participant for follow up after release.	Pre-release	CAU TCAC
Off Study (AD005)	To document discontinued participation in the study due to withdrawal, loss to follow up or end of the study procedures.	Pre-release Post-release	CAU TCAC
Screening, Eligibility & Enrolment (EL001)	To collect screen participant for eligibility, and collect enrolment information.	Pre-release	CAU TCAC

Baseline Demographics (DM001)	To collect participant demographic information at the time of enrolment	Pre-release	CAU TCAC
Demographics Follow-Up (DM002)	To update participant demographic information (where necessary) after correctional facility release.	Post-release	CAU TCAC
Pre-release Assessment (RK001)	To collect information on health and ART history, ASSIST substance use (alcohol and other drugs) screen, PHQ-9 depression screen, social capital, and stigma screens)	Pre-release	CAU TCAC
Post-release Assessment (RK002)	To collect information on health and ART history, ASSIST substance use (alcohol and other drugs) screen, PHQ-9 depression screen, social capital, and stigma screens)	Post-release	CAU - Day 30 visit TCAC- at first session
Routine Health Screening (RK003)	To closely monitor participant health status in order to guide referrals and session services following established study algorithms (includes symptom screen, and weight measurements).	Post-release	TCAC
Health Seeking (SS001)	To collect information on self-reported visits to access medical or non-medical HIV care and treatment services at any time after correctional centre release.	Post-release	CAU TCAC
Clinic Visit (SS002)	To collect details of self-reported participant clinic visits.	Post-release	CAU TCAC

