## 5.2 Schedule of case report forms

Table 6: Schedule of data collection within correctional facility

Case Report Form	Form Code	Visits:	Visit 1 Enrolment	Visit 2 Pre-release
		Visit Code:	01.0	02.0
Screening, Eligibility & Enrolment	EL001		X	
Pre-release assessment	RK001		X	
Baseline Demographics	DM001		X	
Visit Contact Documentation	AD001		X	[X]
Pre-release Locator	AD002		X	
Case Note Abstraction Pre-release	FV001		[X]	[X]

X required CRF, [X] may be required if updated or as necessary

Table 7: Scheduled study visit windows for all participants after release from correctional facility

Case Report Form	Form Code	Visits:	Visit 3 Release	Visit 4 Post- release	Visit 5 Post- release	Visit 6 Post- release	Visit 7  Post-release
		Time since release:	0D	30D	900D	182D	90 days from time of entry
		Visit Code:	03.0	04.0	05.0	06.0	07.0
Release verification	AD003		X				
Post-release locator	AD004			[X]	[X]	[X]	
Demographics Follow-Up	DM002			[X]	[X]	[X]	
Health Seeking	SS001			[X]	[X]	[X]	
Clinic Visit	SS002			[X]	[X]	[X]	
HIV/TB Testing	SS003			[X]	[X]	[X]	

No Clinic Visit	SS004			[X]	[X]	[X]	
Post entry into care	SS005						X
Case Note Abstraction Post-release	FV002			[X]	[X]	[X]	[X]
Off Study	AD002			[X]	[X]	[X]	[X]

X required CRF, [X] may be required if updated or as necessary

Visit 7 only occurs if participant had entered into care by Visit 7

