### 5.3.5 Study limitations

The proposed implementation research has the following limitations:

- The study depends on contact with incarcerated individuals following release. Such individuals may be more likely to come from unstable living situations and may be highly mobile, making follow up a challenge. However, our experience is that released offenders seek re-integration services and are required to provide accurate contact information for the purposes of compliance with parole. Thus we anticipate tracing a high percentage of released offenders.
- Participant self-report regarding lapses in medications and entry into care may introduce bias as participants may favour the most socially acceptable responses. Verification of self-reported entry-into-care using clinic records will be conducted, where possible, for all participants. Data abstraction forms will be submitted to health staff at the health centres

where participants will report to have linked (refer to out-of-correctional facility clinic data abstraction form).

- Follow up and observation of participants in the pre-intervention period (more frequent than current standard of care) may result in modified or improved participant outcomes because of the fact that they are being studied.
- Pre/post assessments that we intend to apply in this study are susceptible to secular trends and to differences in outcome ascertainment. We believe that secular trends in HIV care both in DCS centers and in the public sector will be minimal in terms of HIV care in correctional centers, care in the community, and the offender population. To account for potential population differences we will include disease state and personal characteristics in the logistic regression analysis.
- A low proportion participating would markedly reduce the generalizability of the results (pre and post-intervention). Our experience is with an interest and willingness of inmates to participate in studies. Thus we do not anticipate this to be a significant limitation.

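### The primary effectiveness comparison is described in three ways, and none names the pre-release substance use, social capital and stigma scores collected on all participants

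*Combined protocol and SAP*

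**What the plan says.** Three places describe how the arms are compared on the primary outcome.

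- Table 3 lists self-reported care at six months by arm with "Test of proportions (chi-square", unadjusted and without a facility term.
- Section 4.2.2 specifies an intention-to-treat comparison by "mixed effects logistic regression with correctional facility included as a mixed effect". Facility is the only term named besides arm.
- Section 5.3.5 (Study limitations) says "we will include disease state and personal characteristics in the logistic regression analysis". It names no variable. The reason given is that "Pre/post assessments that we intend to apply in this study are susceptible to secular trends", with possible differences between populations.

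On baseline data, section 2.5 says: "In addition the ASSIST substance use tool, social capital questionnaire, and stigma index will be used with all participants". Table 5 places on form RK001 (pre-release, both arms) the "ASSIST substance use (alcohol and other drugs) screen, PHQ-9 depression screen, social capital, and stigma screens". Table 6 marks RK001 with a plain X at enrolment, which its key defines as required: "X required CRF, [X] may be required if updated or as necessary".

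On why these scores might matter, section 1.1 lists the themes found in earlier work with ex-inmates: "These include the clinic experience, social capital, stigma, substance use". It then attributes to these barriers the finding that only 44% had ART continuity at six months. Depression is mentioned as well, but with the remark that it has not been evaluated in this setting in South Africa.

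**The concern.** An analyst could follow Table 3, section 4.2.2 or section 5.3.5 and claim in each case to have followed the plan. The three give different estimates from the same data. Under 5.3.5 the covariates would still have to be chosen, and nothing says that they must be chosen before outcomes are seen. Effectiveness is listed as a primary objective (section 1.2), and the pilot is meant to deliver a protocol ready for a full trial, so its effect estimate should not depend on a choice left open.

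The second issue is efficiency. With about 47 and 94 participants expected to have outcomes, the pilot is small. The plan collects baseline measures of factors that its own background links to the care transition, yet names none of them in the analysis. If they predict six-month care, precision already paid for is given up.

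**Working it through.** **1. The three descriptions side by side**

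| Place | Method | Covariates besides arm |
|---|---|---|
| Table 3 | Chi-square | None |
| 4.2.2 | Mixed effects logistic regression | Facility |
| 5.3.5 | Logistic regression | Two unnamed classes; pre/post rationale |

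Sections 2.1 and 2.4.2 describe individual 1:2 randomisation blocked by facility, so the pre/post rationale does not apply to the comparison between arms.

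**2. The plan's own power figure**

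Inputs from section 4.1: 60 CAU and 120 TCAC, rates 0.25 and 0.49, 78% ascertainment, alpha 0.05 (two-sided assumed, since sidedness is not stated), power 80%. The rates are given there for being in care with an undetectable viral load. They are borrowed here for self-reported care.

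- Analysed: 60 × 0.78 = 46.8 and 120 × 0.78 = 93.6.
- Pooled proportion: (0.25 × 46.8 + 0.49 × 93.6) / 140.4 = 0.41.
- SE under no difference: √[0.41 × 0.59 × (1/46.8 + 1/93.6)] = 0.0881.
- SE under the alternative: √[0.25 × 0.75/46.8 + 0.49 × 0.51/93.6] = 0.0817.
- Power = Φ[(0.24 − 1.96 × 0.0881) / 0.0817] = Φ(0.825) = 79.5%.

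This reproduces the stated 80%. The detectable difference is 0.241 against the stated 0.24.

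**3. What adjustment could add**

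The documents give no association between the scores and retention, so the combined correlation ρ is an assumption. Adjustment multiplies both variances by 1 − ρ².

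| Assumed ρ | Variance reduction | Power |
|---|---|---|
| 0 | 0% | 79.5% |
| 0.2 | 4% | 81.2% |
| 0.3 | 9% | 83.3% |
| 0.4 | 16% | 86.3% |
| 0.5 | 25% | 90.0% |

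The gain reaches 5 points at ρ of about 0.35 (84.7%).

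**4. Check by simulation**

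Logistic regressions were simulated with 47 and 93 analysed, 1,500 runs per setting, facility as a fixed term, with and without four equally prognostic scores (one more than the fix below uses).

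| Share of outcome variance explained | Facility only | Facility plus scores |
|---|---|---|
| 0 | 79.8% | 79.3% |
| about 0.04 | 79.2% | 81.1% |
| about 0.10 | 79.2% | 83.0% |
| about 0.19 | 79.6% | 87.2% |

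Type I error was 4.4% to 5.0% with or without the scores. Leaving them out does not invalidate the test, and including useless ones costs about half a point.

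**5. Chance imbalance**

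With 60 and 120 randomised, a standardised baseline difference has SD √(1/60 + 1/120) = 0.158. One score differs by more than 0.25 SD with probability 11.4%. At least one of three does so with probability 1 − (1 − 0.114)³ = 30%, if the scores are independent (an assumption).

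**6. Room for the extra terms**

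Expected events at the borrowed rates: 0.25 × 46.8 + 0.49 × 93.6 = 11.7 + 45.9 = about 58. That supports three extra terms.

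**The case against.** The strongest reply is that nothing here is an error in the randomised comparison. The blocking factor is in the 4.2.2 model, type I error holds without the scores, and ordinary standard errors already allow for chance imbalance. The plan says that this is not an effectiveness study and that its power figures are illustrative. Its stated success criteria are feasibility targets, so no declared decision turns on 80% versus 83%. All of this stands, and it limits the weight of the efficiency argument.

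The prognostic value is also unproven. A reader might infer that the scores are strong predictors of retention. Section 1.1 reports them as themes and barriers, without any measure of strength, and much of the stigma it describes is met after release.

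The 5.3.5 sentence looks like wording left over from a pre/post design; section 6.3 also describes a quasi-experimental comparison. A reader might take 5.3.5 to promise covariates other than these scores. That cannot be shown, because personal characteristics might include them. Section 2.4.2 masks the investigators until all outcome data are collected, so selection after unmasking is a possibility left open and not something the plan proposes. The sentence nevertheless stands in the current text as a commitment, and masking does not supply the missing list.

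Finally, a reader might infer that depression scores are equally secure for everyone at baseline. PHQ-9 appears in Table 5 but not in section 2.5, so its pre-release collection is not settled.

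**Conclusion.** The point holds as a matter of unfixed specification and forgone precision. One primary comparison has three descriptions, and none names three baseline scores that are collected on everyone and that the plan itself treats as relevant.

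It would be tempting to conclude that the facility-only analysis is biased or invalid. The documents and the simulation do not support that.

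The size is modest and conditional: about 2, 4 and 7 power points at assumed correlations of 0.2, 0.3 and 0.4, and essentially none if the scores are not prognostic. This rests on two-sided testing, on 78% ascertainment, and on rates that section 4.1 states for a different endpoint. The inconsistency between the three places does not depend on any of these assumptions. The change is worth making because it costs almost nothing.

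**What to change.** - **4.2.2:** Prespecify one primary model for self-reported care at six months with arm, correctional facility, and the pre-release RK001 ASSIST, social capital and stigma scores. Enter the scores as continuous, with simple imputation of missing baseline values. State whether facility is a fixed or a random term. Report the standardised difference in proportions with its 95% CI, and keep the unadjusted comparison as a sensitivity analysis.
- **PHQ-9:** Add it only once section 2.5 and Table 5 are reconciled on its pre-release collection.
- **Table 3:** Change the primary-outcome row to match 4.2.2.
- **5.3.5:** Delete the covariate sentence or replace it with a reference to the list in 4.2.2.

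The cost is plan wording and a few lines of code, with no new data. The downside is a few extra parameters and little or no gain if the scores predict retention weakly.
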